### **5.3 Concomitant Medications/Treatments**

- The use of any natural/herbal products or other traditional remedies should be discouraged, but use of these products, as well as any medication or vaccine including over-the-counter or prescription medicines, vitamins, and/or herbal supplements that the patient is receiving at the time of enrolment or receives during the study must be recorded along with:
  - Reason for use
  - Dates of administration including start and end dates
  - Dosage information including dose and frequency

- **Anti-emetics/Anti-diarrheal medications**

From screening onwards, should a patient develop nausea, vomiting and/or diarrhea, then these symptoms should be reported as AEs (see section 8) and appropriate treatment of the event given.

**Prohibited Concomitant Medications:**

**Prohibited medication/class of drug:**

Anticancer therapy:	Not permitted while the patient is receiving study medication
Chemotherapy	
Immunotherapy	
Hormonal therapy*	
Radiotherapy (except palliative)	
Biological therapy	
Other novel agents	
Live virus vaccines	Not permitted while the patient is receiving study medication
Live bacterial vaccines	Not permitted while the patient is receiving study medication and during the 30 day follow up period. An increased risk of infection by the administration of live virus and bacterial vaccines has been observed with conventional chemotherapy drugs and the effects with olaparib are unknown.

\*Hormone Replacement Therapy (HRT) is acceptable

**Restricted Concomitant Medications:**

Medication/class of drug:	Usage (including limits for duration permitted and special situations in which it's allowed):
Strong CYP3A inhibitors (examples): itraconazole, telithromycin, clarithromycin, boosted protease inhibitors, indinavir, saquinavir, nelfinavir, boceprevir, telaprevir	Strong and moderate CYP3A inhibitors should not be taken with olaparib. If there is no suitable alternative concomitant medication, then olaparib should be held for the period of concomitant administration for 3 half lives afterwards for a maximum period of up to 4 weeks.
Moderate CYP3A inhibitors (examples): ciprofloxacin, erythromycin, diltiazem, fluconazole, verapamil	

Medication/class of drug:	Usage (including limits for duration permitted and special situations in which it's allowed):
Strong CYP3A inducers (examples): phenobarbital, phenytoin, rifampicin, rifabutin, rifapentine, carbamazepine, nevirapine, enzalutamide and St John's Wort	Strong or moderate CYP3A inducers should not be taken with olaparib.
Moderate CYP3A inducers (examples): bosentan, efavirenz and modafinil	If the use of any strong or moderate CYP3A inducers are considered necessary for the patient's safety and welfare this could diminish the clinical efficacy of olaparib.

 
• CYP3A4 substrates: hormonal contraceptive, simvastatin, cisapride, cyclosporine, ergot alkaloids, fentanyl, pimozide, sirolimus, tacrolimus and quetiapine
 
• CYP2B6 substrates: bupropion, efavirenz
 
• OATP1B1 substrates: bosentan, glibenclamide, repaglinide, statins and valsartan
 
• OCT1, MATE1 and MATE2K substrates: metformin
 
• OCT2 substrates: serum creatinine
 
• OAT3 substrates: furosemide, methotrexate
 
	
If a patient requires use of a strong or moderate CYP3A inducer, then they must be monitored carefully for any change in efficacy of Olaparib
 
Effect of olaparib on other drugs

	Based on limited in vitro data, olaparib may increase the exposure to substrates of CYP3A4, OATP1B1, OCT1, OCT2, OAT3, MATE1 and MATE2K.
	Based on limited in vitro data, olaparib may reduce the exposure to substrates of 2B6.
	Caution should be observed if substrates of these isoenzymes or transporter proteins are co-administered.
Anticoagulant therapy	Patients who are taking warfarin may participate in this trial; however, it is recommended that international normalized ratio (INR) be monitored carefully at least once per week for the first month, then monthly if the INR is stable. Subcutaneous heparin and low molecular weight heparin are permitted.
Palliative radiotherapy	Palliative radiotherapy may be used for the treatment of pain at the site of bony metastases that were present at baseline, provided the investigator does not feel that these are indicative of clinical disease progression during the study period. Study treatment should be discontinued for a minimum of 3 days before a patient undergoes therapeutic palliative radiation treatment. Study treatment should be restarted within 4 weeks as long as any bone marrow toxicity has recovered.

Medication/class of drug:	Usage (including limits for duration permitted and special situations in which it's allowed):
Administration of other anti-cancer agents	Patients must not receive any other concurrent anti-cancer therapy, including investigational agents, while on study treatment. Patients may continue the use of bisphosphonates or denosumab for bone disease and corticosteroids for the symptomatic control of brain metastases provided the dose is stable before and during the study and they were started at least 4 weeks prior to beginning study treatment.

Primary prophylaxis with Granulocyte colony-stimulating factor (G-CSF) is not recommended, however, if a patient develops febrile neutropenia, study treatment should be stopped and appropriate management including G-CSF should be given according to local hospital guidelines. Please note that G-CSF should not be used within at least 24 h (7 days for pegylated G-CSF) of the last dose of study treatment unless absolutely necessary.

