### **9.0 DRUG INFORMATION**

### 9.1 Trabectedin

- Other names for the drug: Yondelis®
- Description: 1 mg sterile lyophilized powder in a single-dose vial.
- Classification - type of agent: alkylating agent
- Mode of action: Trabectedin is an alkylating drug that binds guanine residues in the minor groove of DNA, forming adducts and resulting in a bending of the DNA helix towards the major groove. Adduct formation triggers a cascade of events that can affect the subsequent activity of DNA binding proteins, including some transcription factors, and DNA repair pathways, resulting in perturbation of the cell cycle and eventual cell death.
- Pharmacokinetics: The pharmacokinetics is characterized by a rapid decline phase at the end of the infusion and slower exponential phases. Population pharmacokinetic analyses suggest that the pharmacokinetics of trabectedin is dose-proportional and exposure is time-independent. No accumulation in plasma is observed upon repeated administrations every 3 weeks.

Binding of trabectedin to human plasma proteins was approximately 97%. Steady state volume of distribution exceeds 5000 L. The estimated mean clearance of trabectedin is 31.5 L/hr (50%) and the terminal elimination half-life is approximately 175 hours.

CYP3A is the predominant CYP enzyme responsible for the hepatic metabolism of trabectedin. Trabectedin was extensively metabolized with negligible unchanged drug in urine and feces.

In patients with solid tumors, following a 3-hour and 24-hour intravenous infusion of C-labeled trabectedin, 64% of the total administered radioactive dose was recovered in 24 days with 58% in feces and 6% in urine.

- Side effects: The most common ( $\geq 20\%$ ) adverse reactions are nausea, fatigue, vomiting, constipation, decreased appetite, diarrhea, peripheral edema, dyspnea, and headache. Please refer to the agent's package insert for a comprehensive list of adverse events.
- Special Warnings and Precautions for Use  
Please refer to the agent's package insert
- Drug Interactions: Co-administration of trabectedin with strong CYP3A inhibitors results in increased trabectedin dose. Co-administration with strong CYP3A inducers results in decreased trabectedin dose.
- Storage and stability: Store trabectedin vials in a refrigerator at 2°C to 8°C (36°F to 46°F). Trabectedin is a cytotoxic drug. Follow applicable special handling and disposable procedures.

Trabectedin must be stored in a secure, limited access area.

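### Section 5.3's exception for an unavoidable strong CYP3A inhibitor holds olaparib only and leaves the Day 1 trabectedin infusion unaddressed, although 9.1 says these drugs increase trabectedin

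*Combined protocol and SAP*

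**What the plan says.** The inhibitor row of the restricted-medication table in section 5.3 reads: "Strong and moderate CYP3A inhibitors should not be taken with olaparib. If there is no suitable alternative concomitant medication, then olaparib should be held". The hold lasts "for the period of concomitant administration for 3 half lives afterwards for a maximum period of up to 4 weeks". The row does not say whose half-life is meant and does not mention trabectedin.

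The inducer rows are built the same way. Inducers are to be avoided with olaparib. The exception begins "If the use of any strong or moderate CYP3A inducers are considered necessary for the patient's safety and welfare", warns that olaparib may then be less effective, and says of such patients: "then they must be monitored carefully for any change in efficacy of Olaparib".

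Section 9.1 names CYP3A as the main CYP enzyme in trabectedin's hepatic metabolism and states: "Co-administration of trabectedin with strong CYP3A inhibitors results in increased trabectedin dose" and "Co-administration with strong CYP3A inducers results in decreased trabectedin dose". The word dose appears to mean exposure. No action follows. On warnings and precautions for trabectedin, the section says only: "Please refer to the agent's package insert".

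Exclusions 3.2.15 and 3.2.16 bar strong and moderate CYP3A inhibitors and inducers at entry. Washout before starting treatment is 2 weeks for inhibitors and 3 to 5 weeks for inducers.

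**The concern.** Two parts of the protocol do not meet. Section 9.1 recognises that strong inhibitors raise trabectedin; section 5.3, which tells sites what to do on study, acts on olaparib alone. A coordinator who follows the exception correctly holds the tablets, finds nothing about the infusion, and gives it on schedule.

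The stake is patient safety. Section 1.3 reports that the dose-limiting toxicities of this combination were thrombocytopenia and prolonged neutropenia, with febrile neutropenia also seen. The exception therefore permits a myelosuppressive cytotoxic to be infused alongside a drug that the protocol itself says increases it.

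**Working it through.** This is mainly a comparison of texts, with a small amount of arithmetic on the hold length. The plan gives no figure of its own to reproduce.

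**1. Could olaparib be shorthand for both drugs?** The protocol's usage says not. The palliative radiotherapy row of the same table says study treatment when both drugs are meant. In Table 4 of section 5.2, raised bilirubin or AST/ALT holds both drugs, while raised ALP or CK holds trabectedin only. In Table 2, one form of grade 3 thrombocytopenia interrupts olaparib while trabectedin continues at its current dose next cycle. The drugs are separated on purpose, so the literal reading is the fair one.

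**2. Does avoiding inhibitors with olaparib already protect trabectedin?** By default, yes. Olaparib is taken twice daily without a break, so a patient on treatment should not be on an inhibitor at all. Under the exception this protection lapses: olaparib stops and the inhibitor continues.

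**3. Does anything else require the infusion to wait?**

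| Provision | What it does | Delays trabectedin for an inhibitor? |
|---|---|---|
| 3.2.15 | Exclusion and washout at entry | No; no on-study action |
| 5.2, new-cycle criteria (nine) | Laboratory and toxicity limits | No; a patient with good counts passes |
| 5.2, intercurrent events | Allows interruption; Principal Investigator discussion if restart takes over 4 weeks | Permits delay, does not require it |
| 5.2 and 5.3, febrile neutropenia | Stops study treatment | Only in that setting |
| 6.2, medication review each Day 1 | May detect the inhibitor | No action attached |
| 9.1, package-insert referral | Points outside the protocol | Cannot be checked |

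**4. Hold length against cycle length.** Inputs: hold of up to 4 weeks (5.3); infusion every 21 days (5.1); half-life 14.9 h for olaparib (9.2). For trabectedin, "the terminal elimination half-life is approximately 175 hours" (9.1). Infusions are assumed to be exactly 21 days apart.

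- Longest hold: 4 × 7 = 28 days, which exceeds 21. A full-length hold includes at least one scheduled Day 1. It includes two if the first falls within its first 28 − 21 = 7 days. A hold shorter than 21 days may include none.
- The 28 days also contain the tail after the inhibitor stops, so inhibitor days = 28 − tail, and the tail depends on whose half-life is meant:
  - The inhibitor's own (h hours): tail = 3h. At least 21 inhibitor days remain if 3h ≤ 7 × 24 = 168, that is h ≤ 56 h.
  - Olaparib's: 3 × 14.9 = 44.7 h = 1.9 days, leaving 28 − 1.9 = 26.1 inhibitor days.
  - Trabectedin's: 3 × 175 = 525 h = 21.9 days, leaving 28 − 21.9 = 6.1 days. This tail alone is longer than a cycle, so the rule cannot sensibly be extended to trabectedin on that reading.

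On the first reading (for h up to 56 h) and on the second, a full-length hold puts at least one Day 1 on the inhibitor itself.

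**5. What cannot be computed.** The documents give no frequency for the exception, no typical course length and no size for the change in trabectedin exposure.

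**The case against.** The strongest reply is that little is left uncovered. Entry washout clears the first infusion, the default rule covers routine use, and investigators may already interrupt treatment for an intercurrent condition. Febrile neutropenia, one setting in which an interacting anti-infective might be started, stops study treatment outright. The insert cited in 9.1 may carry the missing instruction. All of this stands and makes the gap narrow. None of it tells a site, within the protocol, to withhold the infusion when the exception is used.

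A reader might infer more than the documents support:

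- **That sites have no instruction at all.** Not shown. What is shown is that 5.3 gives none; the insert is unseen.
- **That the overlap can be expressed as a risk.** Calendar overlap with Day 1 is not exposure. With a half-life near 175 h (175/24 = 7.3 days), trabectedin persists well after Day 1, and nothing supports an assumption about when in the cycle inhibitor courses begin.
- **That moderate agents are equally affected.** Section 9.1 names strong agents only.
- **That the inducer rows carry the same hazard.** Inducers lower trabectedin, so the issue is lost activity. In a single-arm combination, efficacy cannot be attributed to one drug, so monitoring olaparib's effect already amounts to monitoring the combination.
- **That the trial's inference is at risk.** The response endpoint and the two-stage stopping rules are untouched.

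**Conclusion.** The point holds in a limited form. The strong-inhibitor exception stops one of two drugs that the protocol itself describes as affected, and no other provision in the documents requires the infusion to wait. It applies to a strong inhibitor, newly needed on study, with no suitable alternative, overlapping an infusion.

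Its measurable size is only that the longest permitted hold exceeds the dosing interval by 7 days. The clinical size is unknown. The conclusion assumes that sites follow the literal text of 5.3 and that the package insert is not treated as a protocol instruction. If the insert already directs sites to avoid or delay, the change below aligns the two texts. The inducer wording and the unspecified half-life are minor.

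**What to change.** Amend the strong-inhibitor row of 5.3 as follows:

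- Strong CYP3A inhibitors should not be taken with olaparib or trabectedin.
- If one is unavoidable, hold olaparib and also delay the trabectedin infusion until the inhibitor has been stopped and washed out. Three half-lives of the inhibitor is a reasonable example, subject to the trabectedin supplier's advice. State that the inhibitor's half-life is the one meant.
- A delay beyond 4 weeks goes to the Principal Investigator under the existing 5.2 rule for intercurrent events unrelated to toxicity.

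Strong and moderate inhibitors share one instruction, so word the trabectedin clause for strong agents only. As a minor addition, name trabectedin in the strong-inducer row without requiring a washout: the 3 to 5 weeks used at entry, set against a 21-day cycle, could in effect end trabectedin for a patient who needs a long-term inducer.

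The cost is an edit to one table, plus an occasional delayed infusion. The rule cannot help when an inhibitor is started soon after an infusion already given; blood-count monitoring remains the safeguard there.

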#### 5.4 Other Modalities or Procedures

Palliative radiation therapy may be permitted to a non-target lesion while on study treatment upon discussion with the principal investigator.

#### 5.5 Duration of Therapy

In the absence of treatment delays due to adverse events, treatment may continue for up to 18 months on study until one of the following criteria apply:

- Disease progression as defined in Section 7.0
- Inter-current illness that prevents further administration of treatment
- Unacceptable adverse event(s)
- Patient voluntarily withdraws from treatment
- Bone marrow findings consistent with myelodysplastic syndrome (MDS)/acute myeloid leukemia (AML) **OR**
- General or specific changes in the patient's condition render the patient unacceptable for further treatment in the judgment of the investigator

#### 5.6 Off Treatment Criteria

Patients will be removed from protocol therapy when any of the criteria listed in Section 5.5 apply. Document in the source the reason for ending protocol therapy and the date the patient was removed from treatment. All patients who discontinue treatment should comply with protocol specific follow-up procedures as outlined in Section 5.7. The only exception to this requirement is when a subject withdraws consent for all study procedures or loses the ability to consent freely.

#### 5.7 Duration of Follow-Up

Patients will be followed every 3 months for a minimum of 2 years from registration or until study closure or until death, whichever occurs first. As long as the study remains open with patients on treatment, patients will be followed for survival follow up for at least 2 years from the time of registration. If all patients have completed treatment, the study may be terminated for further follow up before the 2 years from registration for survival follow up for the last patients. Patients removed from treatment for unacceptable adverse events will be followed until resolution or stabilization of the adverse event.

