**STUDY SCHEMA**

**STUDY SYNOPSIS**

Title	Phase II Multi-Center Trial of Trabectedin in Combination with Olaparib in Advanced Unresectable or Metastatic Sarcoma
Phase	Phase II
Methodology	Uncontrolled, Open label, Single-arm
Study Duration	3 years
Study Center(s)	Multi-center: 2 centers
Objectives	
Primary Objective:
 
a. To estimate the overall response rate (ORR) of combined trabectedin and olaparib in patients with advanced unresectable or metastatic sarcoma using a primary endpoint of complete + partial response as defined by RECIST 1.1.
 
Secondary Objectives:
 
a. To estimate the median progression-free survival (PFS) and 6-month PFS as defined by RECIST 1.1
 
b. To estimate the median, 1- and 2-year overall survival (OS)
 
c. To describe the safety and tolerability of combined trabectedin and olaparib
 
Exploratory Objectives:
 
a. To characterize next generation sequencing (NGS) findings on available reports from archival tumor samples to identify predictors of clinical response to therapy.
 
b. To evaluate expression of DNA damage repair pathways by IHC in available archival tumor samples and correlate with response to therapy
 
c. To assess the impact of treatment on levels of novel cardiovascular biomarkers, and determine whether levels predict cardiotoxicity

Number of Subjects	
This study will be conducted using a Simon Minimax two-stage design, with an interim analysis for efficacy to be performed after first stage.
 
Cohort 1 (LMS/LPS): First stage – 16 patients, Second stage – additional 10 patients
 
Cohort 2 (other sarcoma histologies): First stage – 13 patients, Second stage – additional 14 patients

Key Inclusion Criteria	
 
• Age <math>\geq</math> 16 years
 
• Advanced unresectable or metastatic sarcoma
 
• Received at least 1 prior standard chemotherapy. For cohort 1 patients, this must have included a prior anthracycline.
 
• Measurable disease by RECIST 1.1
 
• Adequate hematologic, renal, hepatic function
 
• Adequate creatine phosphokinase
 
• ECOG performance status <math>\leq</math> 1
 
• LVEF <math>\geq</math> institutional LLN
 
• Women of childbearing age and men must agree to use adequate contraception from signing informed consent to at least 6 months (females) and 5 months (men) after study drug treatment
 

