### **2.2 Secondary Objectives**

- 2.2.1 To estimate the median progression-free survival (PFS) and 6-month PFS as defined by RECIST 1.1
- 2.2.2 To estimate the median, 1- and 2-year overall survival (OS)
- 2.2.3 To describe the safety and tolerability of combined trabectedin and olaparib

---

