- i. Transthoracic echocardiogram (TTE) will be obtained at baseline to ensure adequate LVEF. Repeat TTE will be obtained every 3 cycles ( $\pm 1$  cycles) while on trabectedin or if clinical concern of decline in ejection fraction. MUGA can be performed if inadequate assessment by TTE per standard practice.
- j. Assessment of cardiovascular biomarkers including suPAR, BNP, high-sensitive troponin-I and high-sensitivity CRP will be obtained at baseline and after 2 doses of trabectedin on cycle 3 day 1.
- k. Results of NGS (if available) and archival tumor tissue to test for the presence of alterations in DNA repair pathways. Patients will not be asked to undergo an additional biopsy to obtain tumor sample. Full reports must be provided by the investigator for documentation on the Patient Safety database. These data are not required to be entered into CRF.
- l. Bone marrow or blood cytogenetic samples may be collected for patients with prolonged hematological toxicities at any timepoint as clinically indicated as defined in Section 5.2. Bone marrow analysis should include an aspirate for cellular morphology, cytogenetic analysis and flow cytometry, and a core biopsy for bone marrow cellularity. If it is not possible to conduct cytogenetic analysis or flow cytometry on the bone marrow aspirate, then attempts should be made to carry out the tests on a blood sample.
- m. Patients will be followed every 3 months via phone for documentation of progression and survival status for a minimum of 2 years from registration. If patient is unavailable, then survival status will be determined if possible, by public available information.
- n. Visits on day 1 of each cycle, lab measurements at days 1, 8 and 15 of each cycle, and the end of treatment visit, can be completed  $\pm 3$  days.

\* Screening labs to be obtained within 14 days of initiation of therapy. Baseline imaging to be obtained within 28 days of initiation of therapy.

\*\* Laboratory assessment will be done on day 8 for first 2 cycles to monitor for cytopenias.

Continued day 8 laboratory assessment beyond cycle 2 is at the discretion of the treating physician.

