#### **11.2 Sample Size and Accrual**

In cohort 1, based on currently available phase III data, the ORR for LMS/LPS subgroup to trabectedin monotherapy (including best response of complete or partial response) is 9% with a 43% clinical benefit rate (CBR). Therefore, we will target a RR of 25% with trabectedin plus olaparib to conclude that combination therapy is meaningful. In stage 1,

we will enroll 16 patients. If  $\leq 1$  patient had an objective response in the first stage, we will terminate the trial early. If  $> 1$  patients have an objective response in the first stage, then an additional 10 patients will be enrolled in stage 2, for a total of 26 patients. If  $\geq 5$  out of 26 patients have an objective response, then we will declare that the combination is promising and worthy of further study. The type 1 error rate is 10% and the power is 80%.

In cohort 2, the ORR is approximately 5% to trabectedin monotherapy. Therefore, we will target a RR of 20% for the combination to be meaningful. In stage 1, we will enroll 13 patients; if zero patients had an objective response, we will terminate the study early. Otherwise, if  $\geq 1$  patient had an objective response, we will enroll an additional 14 patients in stage 2, for a total of 27 patients. If  $\geq 4$  out of 27 patients have an objective response, then we will declare that the combination is promising and worthy of further study. The type 1 error rate is 5% and the power is 80%.

In cohort 1, we require a minimum of 16 patients and a maximum of 26 patients. Assuming we can enroll 2 LMS/LPS patients per month, we will require a minimum of 9 months and a maximum of 14 months to complete accrual. Assuming we will follow the last patient for an additional 24 months, the expected study duration for cohort 1 is expected to be between 33 and 38 months.

In cohort 2, we require a minimum of 13 patients and a maximum of 27 patients. Assuming we can enroll 2 patients with other sarcoma histologies per month, we will require a minimum of 7 months and a maximum of 14 months to complete accrual. Assuming we will follow the last patient for an additional 24 months, the expected study duration for cohort 2 is expected to be between 31 and 38 months.

The total expected duration to complete accrual and follow-up for cohorts 1 and 2 is 33 and 38 months.

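### The follow-up clock, Table 5 and the early-closure permission do not fit the planned 2-year overall survival estimate

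*Combined protocol and SAP*

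**What the plan says.** **What is to be estimated.** Section 2.2 lists median, 1-year and 2-year OS as a secondary objective. Section 11.3 estimates them within each cohort by Kaplan-Meier, with Peto errors and 95% confidence intervals. Section 2.4 starts the OS clock at the start of treatment and censors living patients at last follow-up. Section 5.1 lets treatment start up to 14 business days after registration.

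**How long patients are followed.** Section 5.7 follows patients "for a minimum of 2 years from registration or until study closure or until death, whichever occurs first". It adds: "As long as the study remains open with patients on treatment, patients will be followed for survival follow up for at least 2 years", counted from registration. Once nobody remains on treatment, it then allows an exception: "the study may be terminated for further follow up before the 2 years from registration for survival follow up for the last patients". It does not say who the last patients are. Footnote m of the Time and Events Table (Section 6.2) plans phone contact every 3 months for "documentation of progression and survival status for a minimum of 2 years from registration", with public information as a fallback and no exception for closure. Section 11.2 plans as follows: "Assuming we will follow the last patient for an additional 24 months, the expected study duration for cohort 1" is 33 to 38 months, and that for cohort 2 is 31 to 38 months.

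**Patients who cannot restart.** Table 5 (non-hematologic adverse events) takes a patient who cannot resume within 4 weeks off the study. The text of Section 5.2 takes a patient who cannot start a new cycle within 28 days off study treatment. Section 5.6 keeps everyone who stops treatment in follow-up, except those who withdraw consent for all study procedures or lose the ability to consent freely. Section 5.8 allows off-study withdrawal at the investigator's discretion, including for safety.

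**The concern.** A 2-year survival estimate needs patients still under observation at 24 months on the OS clock. Each of the three rules can remove some of them:

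- The registration clock can stop just before the time point being estimated.
- Table 5, taken at its word, ends survival follow-up for patients who stop because of toxicity. Their prognosis may differ from that of patients who stay, so the censoring may be informative.
- The closure permission can cut follow-up of the later-enrolled patients, while footnote m tells sites that 2 years is an unqualified minimum.

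At stake is the precision of 2-year OS and, for Table 5, possibly its validity. The chosen error formula makes the first matter more than usual, because the Peto error depends directly on the number still at risk at 24 months.

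**Working it through.** **1. The plan's own durations.** At 2 patients a month, cohort 1 needs 16/2 = 8 to 26/2 = 13 months (9 and 14 stated). Adding 24 gives 32 to 37 months (33 and 38 stated, one month more). Cohort 2 needs 13/2 = 6.5 to 27/2 = 13.5 months, rounded to 7 and 14; adding 24 gives 31 and 38, as stated. So 11.2 already budgets for 24 months after the last patient.

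**2. The clock.** 14 business days is 14/5 × 7 = 19.6 calendar days, or about 0.65 month. A patient observed for exactly 24 months from registration has 23.35 to 24 months on the OS clock. Anyone who starts after the registration day and is followed only for the minimum is not at risk at 24 months. Three-monthly contacts counted from registration give the same result: the eighth falls at month 24 (8 × 3), before the OS time point, and the ninth at month 27.

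**3. Table 5.** No arithmetic is possible. The documents give neither the proportion of patients who would leave this way nor their survival relative to the others. Side by side, Table 5 says off study, 5.2 says off treatment for a comparable failure to restart, and 5.6 says follow-up continues. A site cannot satisfy both Table 5 and 5.6 as written.

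**4. Early closure.** The documents give no median OS, so it is assumed.

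Formula: Peto SE = S√((1−S)/r), where S is 2-year OS and r is the number at risk at 24 months.

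Hand calculation for cohort 1, with 26 patients entering evenly at 2 a month and an assumed median of 14 months:

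- S = 0.5^(24/14) = 0.305.
- Full follow-up: r = 26 × 0.305 = 7.9. The 95% half-width is 1.96 × 0.305 × √(0.695/7.9) = 0.177.
- Closure 18 months after the last entry leaves 14 of 26 patients with 24 months of potential follow-up: r = 14 × 0.305 = 4.3. The half-width is 1.96 × 0.305 × √(0.695/4.27) = 0.241.
- Ratio: √(26/14) = 1.36.

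Simulation of this fixed schedule gives Peto 0.173 rising to 0.241 (+39%) and Greenwood 0.173 rising to 0.184 (+6%).

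The ratio depends mainly on accrual time A, roughly √(A/(A−6)). The simulations below use staggered entry in both cohorts, a start lag of 0–0.65 month, assumed median OS of 12–18 months, and closure about 18 months after the last treatment start:

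| Accrual, cohort 1 | √(A/(A−6)) | Simulated mean increase, Peto SE |
|---|---|---|
| 13 months | 1.36 | about 38–41% |
| 14 months | 1.32 | about 35% or slightly more |
| 19.5 months (50% longer) | 1.20 | about 21–22% |

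The Greenwood increase is about 3–8% across these settings. At 13 months' accrual about 12 of 26 patients lack 24 months of potential follow-up (deaths included). With exponential survival, about 3.5–5.8 patients are at risk at 24 months, against 6.4–10.4 with full follow-up.

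**The case against.** Section 5.7 is the governing follow-up section, and its permission is open, conditional and evidently deliberate. Footnote m is a schedule note, and 11.2 states an assumption, not a rule. The estimate affected is descriptive, with no decision attached. Most of the widening comes from the Peto formula: by Greenwood the half-width moves by about one percentage point (0.173 to 0.184). Keeping the study open has a real cost. All of this stands, and it is why the closure permission is a trade-off rather than an error.

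Two years is also only a minimum, so the 3-week shortfall arises only if a site treats it as a stop date. That is true, but nothing in 5.7 or footnote m prevents it. On Table 5, one may answer that 5.6 already requires follow-up and that 5.8 allows withdrawal for safety. But 5.8 gives discretion, whereas Table 5 is worded as automatic.

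A reader might infer more than the documents support:

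- *That early closure biases OS or weakens the response decision.* Closure is administrative censoring by calendar date, so Kaplan-Meier is not biased by it, and the two-stage rules count responses.
- *That the study could close as soon as the last patient stops drug.* Section 5.7 alone sets no floor, but Section 2.4 needs a response window of at least 18 months from start of treatment.
- *That the synopsis entry "Study Duration 3 years" is a conflict.* Thirty-six months lies within 31–38.
- *That Table 5 produces a bias of known size.* The documents hold no inputs for one.

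**Conclusion.** The point holds in three parts of unequal weight.

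- **Clock.** A real mismatch, up to about 3 weeks per patient, which matters for anyone followed only for the stated minimum.
- **Table 5.** A real contradiction with 5.2 and 5.6. Informative censoring is possible, but its size cannot be established.
- **Closure.** Sections 5.7 and 6.2 give sites different rules. If the permission is used about 18 months after the last treatment start, the planned Peto standard error of 2-year OS rises by about 35–41% at 13–14 months' accrual, and by about 21–22% if accrual takes 50% longer. Greenwood's rises by about 3–8%.

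These sizes rest on an assumed median OS of 12–18 months, the accrual patterns shown and full enrolment. The response-rate decision is unaffected.

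**What to change.** 1. **Clock.** In 5.7 and footnote m, set the minimum as death or 24 months from start of treatment, with the last status check on or after that date, using the phone or public-record checks already planned. Cost: wording, and at most about 0.65 month per patient.
2. **Table 5.** Reconcile it with 5.2, 5.6 and 5.8, so that stopping study drug for toxicity does not by itself end progression and survival follow-up. Change no dosing or stopping rule. Cost: wording.
3. **Closure.** Reconcile 5.7 with footnote m, preferably by keeping the 24-month minimum that 11.2 already budgets. Cost: at planned accrual the study closes at about 38 months rather than about 31.5, so about 6 months later, with continued quarterly reports to the monitoring committee and monitoring visits at least yearly. Slow accrual would lengthen this.

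If the sponsor keeps early closure, 5.7 should define the last patients and allow closure no earlier than the end of the 18-month response window in 2.4. Footnote m should carry the same exception, and 11.3 should report the number at risk at 24 months with a Greenwood interval beside the Peto one.
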